11.6 Reporting to the Food and Drug Administration (FDA)

- N/A

11.7 Reporting to the NIH Office of Biotechnology Activities (OBA)

- N/A

11.8 Reporting to the Institutional Biosafety Committee (IBC)N/A

- N/A

11.9 Reporting to Hospital Risk Management

- Participating investigators will report to their local Risk Management office any subject safety reports or sentinel events that require reporting according to institutional policy.

11.10 Monitoring of Adverse Events and Period of Observation

- All adverse events, both serious and non-serious, and deaths that are encountered from initiation of study intervention, throughout the study, and within 30 days of the last study intervention should be followed to their resolution, or until the participating investigator assesses them as stable, or the participating investigator determines the event to be irreversible, or the participant is lost to follow-up. The presence and resolution of AEs and SAEs (with dates) should be documented on the appropriate case report form and recorded in the participant's medical record to facilitate source data verification.
- For some SAEs, the study sponsor or designee may follow-up by telephone, fax, and/or monitoring visit to obtain additional case details deemed necessary to appropriately evaluate the SAE report (e.g., hospital discharge summary, consultant report, or autopsy report).
- Participants should be instructed to report any serious post-study event(s) that might reasonably be related to participation in this study. Participating investigators should notify the DF/HCC Overall Principal Investigator and their respective IRB of any unanticipated death or adverse event occurring after a participant has discontinued or terminated study participation that may reasonably be related to the study.

CONFIDENTIAL

This document is confidential. Do not disclose or use except as authorized.

12. DATA AND SAFETY MONITORING

CONFIDENTIAL

This document is confidential. Do not disclose or use except as authorized.

12.1 Data Reporting

Method

After review and approval by the QACT manager, [name], the decision was made that QACT will not collect, manage, or monitor data for this study. Note that this is not a therapeutic drug trial. The research activity involves only the IV administration of the PET radiopharmaceutical N-13 Ammonia or FDG. Instead, data will be collected and managed by the P.I. using a REDCap database.

12.2 Safety Meetings

- The DF/HCC Data and Safety Monitoring Committee (DSMC) will review the protocol up to four times a year to review toxicity and accrual data. Information to be provided to the committee may include: up-to-date participant accrual; current dose level information; all grade 2 or higher unexpected adverse events that have been reported; summary of all deaths occurring within 30 days of intervention; any response information; audit results, and a summary provided by the study team. Other information (e.g. scans, laboratory values) will be provided upon request.

12.3 Monitoring

- Involvement in this study as a participating investigator implies acceptance of potential audits or inspections, including source data verification, by representatives designated by the DF/HCC Overall Principal Investigator (or Protocol Chair) or DF/HCC. The purpose of these audits or inspections is to examine study-related activities and documents to determine whether these activities were conducted and data were recorded, analyzed, and accurately reported in accordance with the protocol, institutional policy, Good Clinical Practice (GCP), and any applicable regulatory requirements.
- All data will be monitored for timeliness of submission, completeness, and adherence to protocol requirements. Monitoring will begin at the time of participant registration and will continue during protocol performance and completion.

13. REGULATORY CONSIDERATIONS

CONFIDENTIAL

This document is confidential. Do not disclose or use except as authorized.

13.1 Protocol Review and Amendments

- This protocol, the proposed informed consent and all forms of participant information related to the study (e.g., advertisements used to recruit participants) and any other necessary documents must be submitted, reviewed and approved by a properly constituted IRB governing each study location.
- Any changes made to the protocol must be submitted as amendments and must be approved by the IRB prior to implementation. Any changes in study conduct must be reported to the IRB. The DF/HCC Overall Principal Investigator (or Protocol Chair) will disseminate protocol amendment information to all participating investigators.
- All decisions of the IRB concerning the conduct of the study must be made in writing.

13.2 Informed Consent

All participants must be provided a consent form describing this study and providing sufficient information for participants to make an informed decision about their participation in this study. The formal consent of a participant, using the IRB approved consent form, must be obtained before the participant is involved in any study-related procedure. The consent form must be signed and dated by the participant or the participant's legally authorized representative, and by the person obtaining the consent. The participant must be given a copy of the signed and dated consent document. The original signed copy of the consent document must be retained in the medical record or research file.

13.3 Ethics and Good Clinical Practice (GCP)

This study is to be conducted according to the following considerations, which represent good and sound research practice:

- E6 Good Clinical Practice: Consolidated Guidance
www.fda.gov/downloads/RegulatoryInformation/Guidances/UCM129515.pdf
- US Code of Federal Regulations (CFR) governing clinical study conduct and ethical principles that have their origin in the Declaration of Helsinki
 - Title 21 Part 11 – Electronic Records; Electronic Signatures
www.access.gpo.gov/nara/cfr/waisidx_02/21cfr11_02.html

CONFIDENTIAL

This document is confidential. Do not disclose or use except as authorized.

- Title 21 Part 50 – Protection of Human Subjects
www.access.gpo.gov/nara/cfr/waisidx_02/21cfr50_02.html
- Title 21 Part 54 – Financial Disclosure by Clinical Investigators
www.access.gpo.gov/nara/cfr/waisidx_02/21cfr54_02.html
- Title 21 Part 56 – Institutional Review Boards
www.access.gpo.gov/nara/cfr/waisidx_02/21cfr56_02.html
- Title 21 Part 312 – Investigational New Drug Application
www.access.gpo.gov/nara/cfr/waisidx_02/21cfr312_02.html
- State laws
- DF/HCC research policies and procedures
<http://www.dfhcc.harvard.edu/clinical-research-support/clinical-research-unit-cru/policies-and-procedures/>

It is understood that deviations from the protocol should be avoided, except when necessary to eliminate an immediate hazard to a research participant. In such case, the deviation must be reported to the IRB according to the local reporting policy.

13.4 Study Documentation

- The investigator must prepare and maintain adequate and accurate case histories designed to record all observations and other data pertinent to the study for each research participant. This information enables the study to be fully documented and the study data to be subsequently verified.
- Original source documents supporting entries in the case report forms include but are not limited to hospital records, clinical charts, laboratory and pharmacy records, recorded data from automated instruments, microfiches, photographic negatives, microfilm or magnetic media, and/or x-rays.
- Photographs may be taken during the ablation procedures for illustration purposes in scientific publications or meetings, however, such photographs will not include the patient's face and will not in any way identify the patient.

13.5 Records Retention

- All study-related documents must be retained for the maximum period required by applicable federal regulations and guidelines or institutional policies.

CONFIDENTIAL

This document is confidential. Do not disclose or use except as authorized.

13.6 Multi-center Guidelines – N/A

***13.7 Cooperative Research and Development Agreement (CRADA)/Clinical
Trials Agreement (CTA) – N/A***

CONFIDENTIAL

This document is confidential. Do not disclose or use except as authorized.

14. STATISTICAL CONSIDERATIONS

14.1 Study Design/Endpoints

Arm 2: Study design/endpoints are identical for Arms 1 & 2.

In this study of patients with liver lesions, it is expected that roughly two-thirds of patients will have FDG-avid tumors, one-third of patients will have non FDG-avid tumors, and although it is possible for a patient to have both types of tumor, that is considered rare. For sample size and power considerations we therefore conservatively assume that patients will have one type of tumor or the other and therefore target a sample size of 100 patients per arm, allowing for the potential for renal insufficiency in up to 25% of all patients (described in more detail below). Also, as the techniques focus on analysis by tumor and it is estimated that 70% of patients will have only a single lesion, the sample size considerations will focus on enrolling *patients* rather than *tumors*. Multiple tumors per patient, when they occur, will be treated and assessed in the statistical analysis, with appropriate adjustment for clustering of tumors within a patient to account for correlation of responses within a patient. Sample size considerations, however, focus on enrollment of patients. The study design and endpoints are identical for Arm 1 and Arm 2.

Primary Objectives:

1. Among FDG-avid liver tumors, comparison of imaging techniques will be done on paired tumor samples using McNemar's test, focusing on discordant pairs (AP-PET-1 adequate/CECT inadequate and AP-PET-1 inadequate/CECT adequate). For these comparisons it is expected that the rate of discordance will be high (near 60% of all pairs) and that differential in discordance will be large (difference between discordant pairs on the order of 50% or higher). In addition to comparing discordant pairs, there is interest in being able to precisely estimate the visibility rates under each imaging modality. With 50 paired samples in the FDG-avid liver tumor ablation group in each arm, visibility of the entire ablation margin can be estimated with a 95% binomial confidence interval that should be no wider than 24 percentage points (+/- 12%) in the expected range of visibility of each modality (80% for AP-PET and 20% for CECT). This sample size will provide greater than 90% power for McNemar's test using a 5% type I error given the assumptions above about discordance.

Since both imaging modalities are required for McNemar's test and the rate of renal insufficiency that would preclude a paired CECT scan is estimated to be roughly 25%, inflation for loss due to patients with renal insufficiency implies that the FDG-avid tumor target sample size for this trial is 67 patients per arm ($=50/0.75$). The trial will be monitored closely for

CONFIDENTIAL

This document is confidential. Do not disclose or use except as authorized.

potential early closure if the rate of renal insufficiency is lower than 25% or potential extension of accrual if the yield of paired samples is lower than 75%.

2. With at least 50 evaluations in the FDG-avid liver tumor treated group per arm, the visibility rates for AP-PET-1 and intra-procedural PET/CECT will be estimated with an accuracy of +/- 12% using 95% confidence intervals for binomial proportions. With this sample size, if the observed visibility rate is near 90%, the 95% confidence interval width is expected to be shorter than 19 percentage points.

3. In patients with FDG-avid liver tumors, the goal of this objective is to assess the proportion of cases confirmed to have adequate ablation margins using 24-hour MRI or CT as the gold standard among those identified as nominally adequate at the time of final intra-procedural imaging. Note that for this objective, patients do not have to receive intra-procedural iodinated IV contrast, hence the reduction in sample size due to renal insufficiency does not apply to this objective. It is expected that nearly 95% of cases will be identified as nominally adequate by all available post-ablation intra-procedural imaging data (i.e. standard-of-care imaging plus AP-PET). With 75 cases per arm, this translates to roughly 71 nominally adequate cases. Among these cases, the ablation margin adequacy rates based on 24-hour MRI or CT will be estimated with 95% binomial confidence intervals and it is expected that the adequacy rates for all available post-ablation intra-procedural imaging will be high, in the range of 90% or higher. With the sample size stated above, the 95% confidence intervals to confirm adequate ablation after 24 hours will be no wider than 16 percentage points (+/- 8%). It is also of interest to confirm that margins that were deemed inadequate on AP-PET alone were confirmed inadequate based on 24-hour MRI or CT but this objective is largely exploratory since the sample size for cases labeled inadequate after AP-PET is expected to be very low, only 5% of the total cases. Finally, it is of interest to assess agreement of final intra-procedural AP-PET with 24-hour MRI or CT. Concordance rates are unknown but are estimated to be in the range of 50 to 80%. With 75 cases per arm, the 95% confidence intervals on the concordance rates are expected to be no wider than 24 percentage points (+/- 12%) assuming, conservatively, that the true concordance rate is near 50%.

4. Among non FDG-avid tumors (expected to be one-third of patient accrual) comparison of imaging techniques will be done on paired samples using McNemar's test, focusing on discordant pairs (AP-PET fused to pre-procedural MRI or CT adequate/CECT fused to pre-procedural MRI or CT inadequate and AP-PET fused to pre-procedural MRI or CT inadequate/CECT fused to pre-procedural MRI or CT adequate). For these comparisons it is expected that the rate of discordance will be high (near 70% of all pairs) and that differential in discordance will be large (difference between discordant pairs on the order of 60%). In addition to comparing discordant pairs, there is interest in being able to precisely estimate the visibility rates under each imaging modality. With 25 paired samples per arm in the non FDG-avid liver tumor ablation group, visibility of the entire ablation margin can be estimated with a 95% binomial confidence interval that should be no wider than 34 percentage points (+/- 17%) in the expected range of visibility of each modality (80% for AP-PET and 20% for CECT). This sample size will provide greater than 90% power for McNemar's test using a 5% type I error given the assumptions above about discordance.

CONFIDENTIAL

This document is confidential. Do not disclose or use except as authorized.

Since both imaging modalities are required for McNemar's test and the rate of renal insufficiency that would preclude a paired CECT scan is estimated to be roughly 25%, inflation for loss due to patients with renal insufficiency implies that the non FDG-avid tumor target sample size for this trial is 33 patients per arm ($=25/0.75$). The trial will be monitored closely for potential early closure if the rate of renal insufficiency is lower than 25% or potential extension of accrual if the yield of paired samples is lower than 75%.

5. In patients with non FDG-avid liver tumors, the goal of this objective is to assess the proportion of cases confirmed to have adequate ablation margins using 24-hour MRI or CT as the gold standard among those identified as nominally adequate at the time of final intra-procedural imaging. Patients evaluated for this objective do not have to receive intra-procedural iodinated IV contrast. It is expected that nearly 95% of cases will be identified as nominally adequate by all available post-ablation intra-procedural imaging data (i.e. standard-of-care imaging plus AP-PET). With 33 cases per arm, this translates to roughly 31 nominally adequate cases. Among these cases, the ablation margin adequacy rates based on 24-hour MRI or CT will be estimated with 95% binomial confidence intervals and it is expected that the adequacy rates for all available post-ablation intra-procedural imaging will be high, in the range of 90% or higher. With the sample size stated above, the 95% confidence intervals to confirm adequate ablation after 24 hours will be no wider than 24 percentage points ($\pm 12\%$). It is also of interest to confirm that margins that were deemed inadequate on AP-PET fused to pre-procedural MRI or CT were confirmed inadequate based on 24-hour MRI or CT but this objective is largely exploratory since the sample size for cases labeled inadequate after AP-PET fused to pre-procedural MRI or CT is expected to be very low, only 5% of the total cases. Finally, it is of interest to assess agreement of final intraprocedural AP/FDG PET fused to pre-procedural MRI or CT with 24-hour MRI or CT. Concordance rates are unknown but are estimated to be in the range of 50 to 80%. With 33 cases per arm, the 95% confidence intervals on the concordance rates are expected to be no wider than 36 percentage points ($\pm 18\%$) assuming, conservatively, that the true concordance rate is near 50%.

Secondary Objectives:

Within arm, comparison of local tumor progression rates to ablation margin adequacy will be largely descriptive as this study does not have adequate power to make definitive conclusions about progression rates. Given the expected heterogeneity of the treated liver tumor populations at presentation and potential variability in clinical follow-up for local progression, this objective is therefore largely exploratory. Intra-procedural IV iodinated contrast is not required for patients analyzed for this objective. An independent radiologist will perform blinded reads for both the final intraprocedural AP-PET and 24-hour MRI or CT to classify cases as adequate or inadequate with respect to the ablation margins for both imaging techniques. Cases will be followed clinically for at least 3-12 months to identify local tumor progression. The method of Kaplan and Meier will be used to estimate the censored time-to-failure distributions for local tumor progression with the goal of estimating, in a preliminary and exploratory fashion, the local tumor progression rates by adequacy of the blinded AP-PET and 24-hour MRI or CT reads. Statistical

CONFIDENTIAL

This document is confidential. Do not disclose or use except as authorized.

precision will be limited for these evaluations and no formal comparison of groups will be performed.

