The ablation will be planned and the ablation applicators inserted percutaneously using routine FDG PET/CT and possible supplemental US guidance. The ablation will then be performed using current protocols with either microwave ablation or cryoablation devices. Microwave ablation and cryoablation devices offer complimentary advantages that enable us to safely and effectively treat many liver tumors. Cryoablation may be better tolerated and less painful when ablating liver tumors close to the liver capsule or diaphragm. The iceball created during cryoablation is usually well visualized during the ablation, which can offer safety advantages when ablating near critical structures. Microwave ablation has fewer tendencies to induce thrombocytopenia or myoglobinemia than cryoablation, which can be an advantage in patients with baseline thrombocytopenia or renal insufficiency. Microwave ablation is better able to overcome vascular heat-sink phenomena that can limit the ablation of tumor cells abutting large blood vessels. Our standard practice is to choose the most appropriate ablation technology based on the individual patient's specific circumstances. Radiofrequency ablation is not included in this protocol, as microwave ablation has almost completely replaced the use of radiofrequency ablation in our practice.

[figure not shown]
When the initial ablation is completed, intra-procedural AP-PET-1 (research scan #1) will be performed and the findings recorded. Specifically, the ablation margin separating the FDG-avid tumor from the normal ammonia-perfused liver will be assessed for visibility and thickness along the entire circumference. Patients with adequate renal function (EGFR >60) will then undergo intra-procedural contrast-enhanced CT, as is now performed in routine clinical practice to monitor initial results. Non-contrast CT will be used in cases of inadequate renal function or contrast allergy. If no additional overlapping ablation applications are deemed necessary or appropriate based on routine CT (Pathway 1), the procedure will be concluded at this point. AP-PET information may be used to aid the margin assessment if CT is inconclusive. Note that routine CT will always be used to determine the safety of additional overlapping ablation, per routine clinical practice. This is because proximity of ablation devices to critical structures can only be imaged with CT and not with PET. The patient will then undergo routine 24-hour post-procedure liver MRI

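### The early-closure option in 14.1 tracks only the paired scans of Objectives 1 and 4: using it takes cases from primary Objectives 3 and 5, and its closure and extension triggers are not complements

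*Combined protocol and SAP*

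**What the plan says.** All of the following is in section 14.1 unless stated.

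- **Objective 1** is sized on pairs: "With 50 paired samples in the FDG-avid liver tumor ablation group in each arm". The plan divides 50 by 0.75 to reach 67 FDG-avid patients per arm. Objective 4 does the same for non-avid tumours, with 25 pairs and 33 patients.
- **Closure and extension**, in the same words under Objectives 1 and 4: "potential early closure if the rate of renal insufficiency is lower than 25% or potential extension of accrual", the latter when paired yield is below 75%. No closing number, timing of looks, minimum total or order of priority is given.
- **Objective 3** does not need intra-procedural contrast: "hence the reduction in sample size due to renal insufficiency does not apply to this objective". Its precision is stated for 75 cases, about 71 of them nominally adequate. The limits are 16 points for confirmed adequacy (rate about 90%) and 24 points for concordance (rate 50%).
- **Objective 5** does not need contrast either. Its limit for adequacy is 24 points on about 31 cases, and for concordance: "With 33 cases per arm, the 95% confidence intervals on the concordance rates are expected to be no wider than 36 percentage points".
- **Other causes of a missing pair**, section 1.1: "Non-contrast CT will be used in cases of inadequate renal function or contrast allergy".

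Section 1.2 lists all five as primary objectives.

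**The concern.** The renal rate determines how many treated patients yield a CECT pair. A rate below 25% brings the pairs for Objectives 1 and 4 sooner, which is why the plan considers closing. The same low rate brings no extra cases to Objectives 3 and 5, whose denominators are all treated cases of the tumour type. For them, early closure is only a loss of sample size, and nothing in 14.1 prevents it.

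The two triggers also look at different quantities: closure at the renal rate, extension at paired yield. These would be complements only if renal insufficiency were the sole reason for a missing pair, and section 1.1 names contrast allergy as another. If both conditions are met, the plan does not say which governs.

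At stake are the stated precision of two primary objectives and a monitoring rule that can point both ways.

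**Working it through.** **Inputs (14.1).** Pairs 50 and 25; expected yield 0.75; targets 67 and 33; nominally adequate share 95%; planning rates 90% (adequacy) and 50% (concordance).

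**Step 1: the plan's own figures.** 50/0.75 = 66.7, stated 67. 25/0.75 = 33.3, stated 33. Clopper-Pearson 95% widths, taking x = p × n (fractional where necessary), with normal-approximation (Wald) widths, 2 × 1.96 × √(p(1−p)/n), alongside:

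| Quantity | n | p | Exact | Wald | Stated limit |
|---|---|---|---|---|---|
| Obj. 3 concordance | 75 | 0.5 | 23.6 | 22.6 | 24 |
| Obj. 3 adequacy | 71 | 0.9 | 15.3 | 14.0 | 16 |
| Obj. 5 concordance | 33 | 0.5 | 35.7 | 34.1 | 36 |
| Obj. 5 adequacy | 31 | 0.9 | 24.0 | 21.1 | 24 |

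Rounded up, the exact widths give every stated limit; the Wald widths do not. The exact interval is therefore taken as the plan's method.

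**Step 2: no early closure.** At the FDG-avid target of 67 (0.95 × 67 ≈ 64 nominally adequate), the Objective 3 exact widths are 24.9 and 16.2, already above 24 and 16. At 33 non-avid cases Objective 5 meets both limits.

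**Step 3: closure at the paired counts.** This closing point is an assumption. With renal rate r, cases at closure are 50/(1−r) and 25/(1−r), rounded up; 95% of these are nominally adequate. Exact widths in points, concordance / adequacy:

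| r | Obj. 3 cases (adequate) | Obj. 3 (limits 24 / 16) | Obj. 5 cases (adequate) | Obj. 5 (limits 36 / 24) |
|---|---|---|---|---|
| 20% | 63 (60) | 25.7 / 16.7 | 32 (30) | 36.2 / 24.4 |
| 10% | 56 (53) | 27.3 / 17.9 | 28 (27) | 38.7 / 25.9 |
| 0% | 50 (48) | 28.9 / 18.9 | 25 (24) | 40.9 / 27.6 |

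All four limits are exceeded in each row.

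**Step 4: the two triggers.** With renal rate r and other independent loss x, yield = (1−r)(1−x). At r = 0.20 the closure condition is met, and yield falls below 0.75 once x > 1 − 0.75/0.80 = 6.25%. At r = 0.24 the threshold is 1 − 0.75/0.76 = 1.3%. As an illustration with an assumed x of 8%: 0.80 × 0.92 = 73.6%, so 67 patients give about 49 pairs. The documents give no rate for contrast allergy.

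**The case against.** - **The rule is discretionary.** Both actions are only potential and no closing number is given. A reader might infer that early closure will leave Objectives 3 and 5 short, or that the plan orders accrual both to close and to extend. The text supports neither. The loss arises only if the option is used, and its size depends on when. The purpose of securing 50 and 25 pairs is plain, so closing while pairs are short is not a natural reading. This stands, and it limits the point to an unprotected option and an unresolved overlap.
- **The rule is not the whole cause.** A reader might attribute the entire Objective 3 shortfall to it. Step 2 shows that 0.9 points of the concordance excess and 0.2 of the adequacy excess exist at 67 cases with no closure.
- **The effect is modest.** At r = 20% Objective 5 exceeds its limits by only 0.2 and 0.4 points. On Wald widths at that rate only Objective 3 concordance misses (24.7 against 24). The concordance limits assume 50%; at 80%, the top of the plan's range, even 50 and 25 cases give exact widths of 23.7 and 33.9, inside the limits. A 0% rate is an extreme against an expected 25%. All of this stands as a matter of size.
- **Undelivered tracer doses** might seem a further cause of lost pairs. Section 6 makes patients without the ammonia dose no longer eligible, so they arguably leave the denominator too. Contrast allergy has to carry the argument, at an assumed rate.
- **Power is not affected.** The claim "This sample size will provide greater than 90% power for McNemar's test using a 5% type I error" rests on the pairs, which closure at 50 and 25 would preserve. Objectives 3 and 5 are estimation objectives with no power claim.
- **Timing.** The front-sheet log records Arm 1 closed and then permanent closure to accrual for funding, so a new accrual rule has little operational effect now. The stated widths still matter for reporting.

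**Conclusion.** The concern holds in limited form. The closure option serves Objectives 1 and 4 only, and 14.1 sets no minimum total for Objectives 3 and 5. On the exact method, and assuming closure at exactly 50 and 25 pairs, the widths exceed the stated limits by 0.7 to 1.7 points for Objective 3 and 0.2 to 0.4 for Objective 5 at a 20% renal rate. At 10% the excess is 1.9 to 3.3 and 1.9 to 2.7 points; at 0% it is 2.9 to 4.9 and 3.6 to 4.9. These figures use the plan's planning rates of 50% and 90% and one tumour per patient, as its sizing does; additional tumours could add cases but are not a stated safeguard. The triggers are not complements, but whether both would be met in practice depends on a contrast-allergy rate that the documents do not give.

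**What to change.** In 14.1, items 1 and 4, replace the renal-rate trigger with one counted rule per arm:

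1. Close only when 50 FDG-avid pairs, 25 non-avid pairs, 67 FDG-avid cases and 33 non-avid cases (with or without CECT) have all been reached.
2. Consider extension if the pairs are short at those totals.
3. Restate the Objective 3 widths for 67 cases: about 25 points for concordance and 16.2 for adequacy.

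The rule should name 67, not the 75 on which Objective 3 now relies. 75 + 33 = 108 exceeds the 100 per arm, and with two-thirds of patients FDG-avid, 75 avid cases would need about 113 patients (75 ÷ 2/3 = 112.5).

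If closure at the paired counts is to remain an option, state the exact widths for those counts instead: up to about 29 and 19 points for Objective 3, and 41 and 28 for Objective 5. As accrual is recorded as closed, the report should in any case give exact intervals for the counts achieved.

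The cost is wording, plus either giving up an option to close slightly early or stating slightly wider intervals. The totals of 67 and 33 sum to the existing 100 per arm, so they need no additional patients provided the tumour mix is as expected.
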